This message:
Discourages me wanting to smoke
Makes smoking seem unpleasant to me
Makes me concerned about health effects of smoking

Negative Affect

How much did the label make you feel:
Anxious
Sad
Scared
Guilty
Disgusted

Roswell Park Protocol Number: I 757820

Thinking of Harms

How much did the labels make you think about:
The chemicals in the smoke of the cigarettes
Health problems caused by smoking
The harm your smoking might be doing to you
The harm your smoking might be doing to other people

Would you support or oppose a policy that required this label to appear on cigarette packages?
Strongly oppose – Strongly support

Would you support or oppose a policy that required this label to appear in advertising for cigarettes?
Strongly oppose – Strongly support

Remote Data Collection – EMA Schedule and Questionnaires

3 Daily Reports – 11 am, 4pm, 9pm (assessments < 5min)

How many cigarettes have you smoked since the last prompt?

How many of these cigarettes were research cigarettes?

How many of these cigarettes were not research cigarettes?

How you used any other tobacco products since the last prompt?

If yes: What product? How many times did you use it?

Please record your product weight with the provided scale.

RIGHT NOW: How would you rate your (0 – 100 VAS):

- Craving
- Irritability
- Anxiousness/nervousness
- Difficulty Concentrating
- Stress
- Bored
- Calm/Relaxed
- Happy
- Alert
- Enthusiastic

Provide Reminder to collect all cigarette butts in provided materials, store used pods

11 am Only (additional questions)

Hedonic Attribute Profile: In the past day, how would you rate the research cigarettes (1-7 Likert)

Draw

Irritation

Smoothness

Roswell Park Protocol Number: I 757820

Strength

Tobacco Taste

Similarity to Usual Brand

Product Evaluation Scale (1 - 7 Likert):

Was it satisfying?

Did it taste good?

Did it calm you down?

Did you enjoy the sensations in your mouth?

Did it reduce your craving for a cigarette?

Were there bothersome side effects?

Did you enjoy using the product?

Would you be willing to use the product long term?

Record CO measurement

9pm Only (additional questions):

Record CO measurement

Reflect on today as a whole: How would you rate your (0 – 100 VAS)

- Craving
- Irritability
- Anxiousness/nervousness
- Difficulty Concentrating
- Stress
- Bored
- Calm/Relaxed
- Happy
- Alert
- Enthusiastic

Thinking of the cigarettes you smoked today: How would you rate (0 – 100 VAS)

- Tastes like my own brand

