- Satisfying like my own brand
- Enjoyable like my own brand
- Relieved my cravings like my own brand

2-3 Pseudo-Random Prompts: Between 11 - 4, 4 – 9

Take picture of research cigarette pack

How often did you notice your warning label in the past day?

Have you read or looked closely at the warning label in the past day?

Have you made any effort to avoid looking at or thinking about the warning labels (such as covering them up, keeping them out of site, using a cigarette case, etc.)

Has seeing the warning label stopped you from having a cigarette when you were about to smoke?

Has seeing the warning label affected how you smoke a cigarette?

Has seeing the warning label affected how you hold a cigarette?

Roswell Park Protocol Number: I 757820

Think back on the most recent cigarette you smoked:

Where were you (home, work, other's home, vehicle, bar/restaurant outside, other)

Was smoking permitted (yes, discouraged, no)

Were you with others (yes, no)

- IF YES: Were they: smoking, vaping, both, neither

What activity were you doing (working/chores, inactive/leisure, socializing, eating/drinking, other)

How strong was your craving prior to use?

How many puffs did you take?

Duke Sensory Evaluation (1 – 7 Not at all – Extremely)

- How much did you like the puffs you took?
- How satisfying were the puffs you took?
- How high in nicotine do you think the puffs were?
- How similar to your own brand were the puffs?

Roswell Park Protocol Number: I 757820

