Appendix D: Experimenter Guide

1. Welcome and Introductions:

2. Introduction:

- I would appreciate if you can minimize distractions until our videoconference is done. If something important requires your attention, please let me know and we can take a brief pause.
- First, I'll ask you to complete an online questionnaire. Here, we are looking for some information about you and your tobacco use.
- We will then move onto training you on study procedures.
- There is no right or wrong answer here. You are the expert and we are really interested in your honest responses to questions and to the tasks during the laboratory session.
- Do you have any questions?

*Answer any questions.

3. Baseline Questionnaires

- "We will now begin the baseline questionnaires."
 - Baseline measures and covariates will assess:
 - Demographics (age, sex, race/ethnicity, education, income)
 - Tobacco use behaviors (consumption, brand, menthol preference, quit history)
 - Cognitive and affective measures
 - A series of previously used items will assess knowledge and perceptions of filter vents.^{113,117}
 - Nicotine dependence will be assessed using:
 - Fagerström Test for Nicotine Dependence (FTND;¹¹⁸)
 - Behavioral aspects of cigarette dependence will be assessed using:
 - The Glover-Nilsson scale^{120,121}
 - Questionnaires on vent messages
 - Questionnaires on message perceptions

We will now train you and provide you with supplies for the field study

Field Study Description

For the field study, you are going to use your mobile device to record your cigarette and other tobacco use and answer questions about how you're feeling and the situations in which you use your products. You will be prompted 5 times each day via text message to answer questionnaires. Three of these prompts will be at the same time every day: 11am, 4pm, and 9pm. Two of these prompts will be at a random time each day, one between 11am – 4pm and one between 4pm – 9pm. To receive bonus payment for the field study, you will need to respond to

Roswell Park Protocol Number: I 757820

all 5 prompts. If you fail to respond to prompts for 3 consecutive days, we will send you a warning. If compliance to procedures does not improve, you will be discontinued from the study.

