Please keep track of the amount of cigarettes and other tobacco you use. The scheduled prompts will ask you to report the number of cigarettes you've smoked. The random prompts will ask you to report on the situation in which you last used your product, such as the location and if smoking was allowed. We also ask that you store all used cigarette butts in the provided materials

Here are examples of the questions you will be asked at each assessment (show questionnaires). Do you have any questions?

We are also providing you with a CO monitor that will connect with your phone to take a CO measurement each night (demonstrate use).

We are also providing you with a scale to weigh other tobacco products that you may use, such as an e-cigarette or smokeless tobacco. If you use these other products, we would like you to weigh your product (e.g., pod, tank, dip tin) at the beginning and end of each day. If you are close to finishing your product and may start a new one, please weigh both the older and newer one at the beginning and end of the day.

Two additional times during the field study, we will ask you to videoconference with us as a study check-in and to have you respond to some questionnaires.

These are the cigarettes we are asking you to use during the field study (provide research cigarettes). Please use only these cigarettes and do not tamper with the cigarette pack. At random points in the study, we may ask you to take a picture of the cigarette pack.

Do you understand the procedures for the field study? Please call us if you have any questions.

Videoconferencing Sessions 2 & 3

Hello, today we are going to have you fill out a questionnaire. I will send it to you now. Have you been regularly storing your cigarette butts. Can I see how you are storing them?

Compliance: Your compliance has been great. Thank you!

Or: Your compliance has not met the standards. Please respond to more prompts or you may be discontinued for the study. Do you have any questions about the study procedures that may help you respond to more prompts?

Session 3 only:

Please pack up your supplies to prepare a return shipment. Can I see how you've stored your supplies in the box?

When we receive your materials, we will send you payment for completing the study. Thank you for participating.

Roswell Park Protocol Number: I 757820

Ads for the website/mobile app:

RESEARCH PARTICIPANTS NEEDED

Searching for:
21-69 year old daily cigarette smokers

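### The EMA schedule that feeds the cigarette count (Primary 2) differs between Sections 11.3/11.4 and Appendices C/D, and the count item's look-back is not anchored to the last completed count

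*Combined protocol and SAP*

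**What the plan says.** **Outcome.** Section 3 makes weekly cigarette consumption in the field period Primary 2. Section 11.4 (cigarette tracking via EMA) calls the cigarette total the key field outcome.

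**Schedule in the body.** Section 11.3 has five scheduled questionnaires a day. Section 11.4 fixes them at 11am, 1:30pm, 4pm, 6:30pm and 9pm and says these reports assess consumption. The same paragraph then points to Appendix C for what is asked at each pseudo-random prompt, although it has listed only fixed times.

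**Schedule in the appendices.** Appendix C (Remote Data Collection) has three daily reports, at 11am, 4pm and 9pm. These contain the count item, "How many cigarettes have you smoked since the last prompt", and the other-tobacco item, "How you used any other tobacco products since the last prompt". It adds "2-3 Pseudo-Random Prompts: Between 11 - 4" and 4 to 9, whose question list has no count. Appendix D tells participants "You will be prompted 5 times each day via text message to answer questionnaires" and "Two of these prompts will be at a random time each day". It says that the scheduled prompts take the count and the random ones ask about the situation of use.

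**Missed prompts.** Under Section 11.4 a survey closes after 1 hour and at least 4 of 5 responses is compliant. Section 12.1 writes the 80% requirement as more than 4 of 5. Appendix D says "To receive bonus payment for the field study, you will need to respond to" "all 5 prompts. If you fail to respond to prompts for 3 consecutive days, we will send you a warning".

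**The concern.** Appendix D uses the word prompt for all five daily contacts. A participant who has just answered a random prompt and takes the 4pm or 9pm item at its word will count only from that random prompt. Cigarettes smoked between the previous count report and the random prompt are then never asked about. The 11am report is unaffected, because the contact before it is the 9pm count.

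The second gap exists on either schedule: the item does not say whether the last prompt is the last one sent, the last one answered or the last one that carried a count. Missed prompts are to be expected, since windows are short and Section 11.4 allows one miss a day.

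Two things are at stake: an undercount of Primary 2, and extra between-person variation if some participants read the item one way and some the other. Three sites would be training participants from these texts.

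**Working it through.** The plan gives no figure for this error, so there is none to reproduce. The sizes below are illustrations.

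**Inputs from Section 22.1:** planned difference 3.9 CPD, stated as 25%, so the implied reference mean is 3.9/0.25 = 15.6 CPD and the other arm's is 15.6 - 3.9 = 11.7; SD 7.6. Planned standardized effect: 3.9/7.6 = 0.513.

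**Assumptions not in the documents:** smoking spread evenly over a waking day of W = 14 to 18 h; random prompts uniform within 11am-4pm and 4pm-9pm.

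**1. Contacts and counts per day**

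| Source | Fixed | Random | Count asked at |
|---|---|---|---|
| 11.3 / 11.4 | 5 | none listed | 5 as worded; 3 if the 1:30 and 6:30 content follows Appendix C's random prompts |
| Appendix C | 3 | 2-3 | 3 |
| Appendix D | 3 | 2 | 3 |

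With three random prompts Appendix C gives six contacts, while the compliance rules use five as the denominator.

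**2. Literal look-back, Appendices C/D, nothing missed**
- Two random prompts: expected loss 2.5 h per window, so L = 2.5 + 2.5 = 5 h. Share: 5/18 = 27.8% to 5/14 = 35.7%, or 4.3 to 5.6 cigarettes at 15.6 CPD.
- Three, two of them in one window: the later of the two falls on average 5 x 2/3 = 3.33 h into the window, so L = 2.5 + 3.33 = 5.83 h. Share: 32.4% to 41.7%.
- If the participant reports since the last completed count: 0.

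**3. Mixed readings, ignoring missed prompts.** A share p of participants reads literally, independently of arm. Recorded count = true count x M, with M = k = 1 - L/W for that share and 1 otherwise. Put m1 = 1 - p(1 - k) and m2 = 1 - p(1 - k²). The arm difference is 3.9·m1. The variance in an arm with mean μ is m2(7.6² + μ²) - m1²μ². Then d = 3.9·m1 / √(average of the two arm variances).

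Example, L = 5, W = 14, p = 0.61: k = 0.643, m1 = 0.782, m2 = 0.642; variances 44.5 and 41.2, average 42.9; d = 3.9 x 0.782/√42.9 = 0.466.

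Lowest d over p from 0 to 1:

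| L (h) | W (h) | p | d | Fall from 0.513 | N ratio (0.513/d)² |
|---|---|---|---|---|---|
| 5 | 14 | 0.61 | 0.466 | 9.2% | 1.21 |
| 5 | 16 | 0.59 | 0.478 | 6.8% | 1.15 |
| 5 | 18 | 0.58 | 0.486 | 5.3% | 1.11 |
| 5.83 | 14 | 0.63 | 0.447 | 12.9% | 1.32 |
| 5.83 | 16 | 0.61 | 0.464 | 9.6% | 1.22 |
| 5.83 | 18 | 0.60 | 0.475 | 7.4% | 1.17 |

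At p = 0 or p = 1, d stays at 0.513, because a uniform proportional loss scales mean and SD alike.

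**4. A missed prompt**
- Five fixed counts, look-back to the last prompt sent: one miss loses 2.5 h, or 15.6 x 2.5/18 to 15.6 x 2.5/14 = 2.2 to 2.8 cigarettes. For a missed 11am report the loss is W - 10 = 4 to 8 waking hours (4.5 to 6.9 cigarettes). Look-back to the last prompt answered loses 0.
- Appendices C/D, look-back to the last prompt answered: if the 4pm report is missed and the evening random prompt answered at 6:30pm on average, the 9pm report covers only from then. The stretch from 11am to 6:30pm, 7.5 h, goes uncounted.
- Only a look-back to the last completed count gives 0 on both schedules.

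The 7.5 h includes smoking already counted as lost in step 2, so these figures overlap and must not be added.

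**The case against.** The strongest reply is that practice will be better than the wording. Section 11.4 defers to Appendix C, and Appendix D agrees with it on three fixed count reports. Staff train participants, show them the questions and tell them "Please keep track of the amount of cigarettes and other tobacco you use". Many will report since their last count, which loses nothing. If all five reports in Section 11.4 carry the count, the intervening-prompt gap disappears. This stands, and it is why the losses are conditional. It does not close the gap: the training script contains no definition of the look-back, and the missed-prompt question survives on either schedule.

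Four stronger readings are tempting and not supported:
- A reader might set the 4.3 to 5.6 cigarettes a day against the planned 3.9 CPD difference. An undercount common to all arms is not an error of that size in the contrast, and nothing in the documents suggests that reading or response differs by arm.
- A reader might infer that missed smoking is unrecoverable. CPD is collected at the video sessions (Section 5.1) and butts and unused product are retained (Section 11.3). What is missing is a rule linking them to the EMA count.
- The Session 1 instruction to record each smoking event might look like a third counting scheme. It refers to the detail that follows and is better taken as loose wording.
- The more-than-4-of-5 in Section 12.1 might look like a deliberate third compliance rule. Beside 80% it may simply be a lost ≥ sign.

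**Conclusion.** The point holds and should be fixed. Current passages disagree on the number and timing of contacts and on which of them carry the count, and the item that generates Primary 2 has no defined look-back. On the appendix schedule its literal reading loses about 5 h a day with two random prompts (28-36%) or 5.8 h with three (32-42%); the intended reading loses none.

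The harm is an undercount of the absolute level of Primary 2 and, with mixed readings, a fall in the standardized effect from 0.51 of up to about 9% (N ratio 1.21) or 13% (d 0.447, N ratio 1.32). Those maxima rest on even smoking, a 14 h waking day, the least favourable mix of readings, reading independent of arm, an unadjusted comparison and no missed prompts, so they are not bounds on every case. Missed count reports can add to the loss. No between-arm bias is shown. How many participants would read the item literally is unknown.

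**What to change.** 1. Reword the cigarette item to *since you last reported your cigarettes (at [time of last completed report])*, and the other-tobacco item in the same way. This removes both the intervening-prompt and the missed-prompt ambiguity.
2. State one schedule, and which prompts carry the count, identically in Sections 11.3 and 11.4 and Appendices C and D.
3. State how the reports are summed into Primary 2, and use the CPD given at video Sessions 2 and 3 as a check on the weekly EMA totals. These data are already collected.
4. Secondary drafting: reconcile the compliance wording in Section 11.4, Section 12.1 and Appendix D, and the event-recording wording in Session 1.

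The cost is two REDCap items and aligned text, with no added visits or participant burden. A check against returned packs and butts is optional. They come back once, after Session 3, so they can check only the two-week total. Counting butts also takes staff time: at 15.6 x 14 = about 218 per completer, 240 completers would return about 52,000.

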11 PROCEDURES INVOLVED

11.1 Study Design

Examine how filter ventilation messaging influences real-world product use, perceptions of and responses to products, and awareness of filter ventilation.

Roswell Park Protocol Number: I 757820

Cigarettes are not smoked in isolation, but in a broader informational context. Thus, the effects of ventilation on responses to product use must be assessed with respect to product communications. We will conduct a field protocol in which various product messaging will be assessed under real-world product use experiences in terms of consumers' ratings of product appeal, risk perceptions, or change cigarette smoking behavior. We hypothesize that messaging will influence filter ventilation awareness and perceptions, but not behavior change.

Filters from these sessions will be used to examine within-cigarette compensatory smoking behaviors (e.g., vent blocking; mouth level exposure).¹¹⁴⁻¹¹⁶

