Cigarette tracking via EMA: For the field study, the key outcome is the total number of cigarettes smoked. Participants will be asked to complete REDCap questionnaires on their personal phone (iOS or Android). Participants can use the MyCap application to respond to questionnaires. Additionally, REDCap can interface with Twilio, a secure text-messaging platform, to send study related messages and surveys via SMS (text messaging). Proposed EMA methods are based on established best practices. Participants will complete 5 questionnaires every day. These questionnaires will occur at the same time each day: 11am, 1:30pm, 4pm, 6:30pm, and 9pm. These daily reports will be used to assess cigarette and e-cigarette consumption, and 10 items relating to subjective ratings of nicotine withdrawal (e.g., craving, irritability) and mood (e.g., calm/relax, happy). At 11am only, participants will complete selected items from the Hedonic Attribute Profile and Product Evaluation Scale. At 9pm only, participants will be asked to rate the taste, satisfaction,

Roswell Park Protocol Number: I 757820

enjoyment, and craving relief from the cigarettes they smoked that day. Participants will also be asked to take a CO measurement at this time. At the 1:30 and 6:30 prompts, participants will be asked about situational factors related to use (Location, smoking permitted, with others, activity, craving) and complete the Duke Sensory Evaluation scale. Participants also will be asked to take a picture of their research cigarette pack to ensure compliance. Surveys will be open for 1 hour after the scheduled time for completion. Appendix C demonstrates the EMA schedule and the questions asked at each daily report and pseudo-random prompt. Participants can earn up to \$10 for each day of EMA compliance, with compliance being defined as responding to ≥ 4 of 5 daily prompts (up to 14 days, totaling \$140). Studies that used similar methods had $>90\%$ compliance. [189, 190].

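### As listed in Appendix C, the field prompt shows the pack message and asks about the label before the Duke ratings, so field attention and Duke outcomes may overstate the effect of a label met in ordinary use

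*Combined protocol and SAP*

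**What the plan says.** Appendix C, under the remote data collection schedule, describes the prompt headed "2-3 Pseudo-Random Prompts: Between 11 - 4, 4 – 9". Its items are listed in this order:

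1. The pack photo: "Take picture of research cigarette pack".
2. Six label items, beginning with "How often did you notice your warning label in the past day". The others cover reading the label, avoiding it, forgoing a cigarette because of it, and changes in how a cigarette is smoked or held.
3. Six items, plus one conditional, on the most recent cigarette. The last is "How many puffs did you take".
4. Four Duke Sensory items, including liking and "How satisfying were the puffs you took".

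Two other places describe the photo differently. Section 11.4 puts the situational items and the Duke scale at fixed 1:30 and 6:30 prompts and then adds: "Participants also will be asked to take a picture of their research cigarette pack to ensure compliance". It does not mention the six label items, but it refers the reader to Appendix C for the questions at each prompt. The Appendix D script says: "At random points in the study, we may ask you to take a picture of the cigarette pack".

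Section 11.2 puts the message on the front of each pack and leaves the no-message pack unaltered. Section 3 lists the Duke scale among several Primary 1 instruments. Section 1.2 expects messages to lower satisfaction. Section 11.1 says that "various product messaging will be assessed under real-world product use experiences".

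**The concern.** A participant in a message arm who follows the prompt as listed handles and photographs the labelled pack. That participant is then asked whether the label changed how they smoke, and later rates how much they liked the cigarette. Two outcomes are exposed.

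- **Label attention.** The photo comes directly before the noticing item, and photos from earlier prompts can fall inside its past-day window. The study's own request can be counted as noticing. The avoidance item has a related problem, because the photo asks someone who hides the pack to bring it out. The Section 5.1 schedule places attention to messaging only in the field column, so no session measure is free of this.
- **Field Duke ratings.** Every field Duke rating sits in this prompt. Recalling a health message just beforehand could lower reported liking and satisfaction in the message arms, which is the hypothesised direction.

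Everyone gets the same item order, and the Section 22.1 mixed model has no term for prompted viewing. The analysis could not separate this effect from the effect of the label.

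**Working it through.** The plan gives no figure for this point, so there is none to reproduce. The check is of item order, exposure counts, and which outcomes and contrasts are reached.

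**Order.** In Appendix C nothing lies between the photo and the noticing item. Between the label block and the Duke items lie place, permission, company (with a conditional follow-up), activity, craving and puffs. The Duke items rate a cigarette already smoked, so the same-prompt effect on them can only be priming of the rating. Exposure from earlier prompts could carry over.

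**Prompted views.** Section 11.4 and Appendix D both give five prompts a day. Appendix D makes three of them fixed and two random.

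- Two photo prompts a day: 2 × 14 = 28 views. This is a ceiling, because it assumes a photo at both prompts every day.
- Three a day, the top of the Appendix C range: 3 × 14 = 42 views. That needs 3 + 3 = 6 prompts a day, which conflicts with the five stated.
- Section 11.4 counts 4 of 5 prompts as compliant. If the missed prompt were always a photo prompt, 1 × 14 = 14 of the 28 would remain.

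**Natural exposure.** Assume that the pack is handled once per cigarette. The prompted share of handlings is then p / (c + p), with p photo prompts and c cigarettes a day.

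| Cigarettes a day | Source | Cigarettes in 14 days | Share at p = 2 | Share at p = 3 |
|---|---|---|---|---|
| 5 | Section 7.2 minimum | 70 | 2/7 = 29% | 3/8 = 38% |
| 15.6 | Section 22.1: 3.9 / 0.25 | 218 | 2/17.6 = 11% | 3/18.6 = 16% |
| 20 | assumption | 280 | 2/22 = 9% | 3/23 = 13% |

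Prompted views are a minority of handlings throughout. Handling a pack need not mean looking at its front, so the share of actual looks could differ.

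**Outcomes reached.** Field attention and field Duke ratings are reached directly. Satisfaction is also measured in the 11 am Product Evaluation items, in the 9 pm comparison with own brand, and at Sessions 2 and 3, where product evaluation includes the Duke scale. Only carry-over could reach these.

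**Contrasts reached.** No arm is exempted from the photo or the label items, so the general burden is shared. What differs is sight of the message: up to 28 prompted views in each message arm, and none of a study message in the no-message arm. The neutral arm has the same prompt and the same number of views, so contrasts with it are balanced on that count, although the content viewed differs.

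**Mitigation.** No section puts the Duke items ahead of the label block, excludes study-requested viewing from the attention items, or adjusts for it.

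**The case against.** The strongest reply is that the built order is not established. Section 11.4 names the situational items, then the Duke scale, then the photo, which is close to the order one would want. Neither place says that its list is the order of administration. This is a fair caution and makes the point conditional. But Section 11.4 defers to Appendix C for the questions themselves, and Appendix C puts the photo first.

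A second reply is that the photo has a legitimate compliance purpose, and that any repeated question about a label draws some attention to it. Both are true. They argue for keeping the photo and the items, but not for placing them ahead of the Duke ratings.

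A reader might also infer more than the documents support:

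- *That these outcomes reflect forced viewing in place of real-world exposure.* The message is on every pack for two weeks, so prompted views add to natural exposure.
- *That satisfaction outcomes as a whole are compromised.* Several satisfaction measures lie outside this prompt.
- *That a true report of not noticing the label becomes impossible after day 1.* That needs a photo of the pack front at an earlier prompt within the past day, every day. No section says which side is photographed, and Appendix D makes the photo occasional.
- *That differences between messages are hidden.* No response options are given for the noticing item, and a similar increment in all three message arms would largely cancel between them. A masking floor or ceiling is possible but not shown.

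**Conclusion.** The concern holds in a limited form. If the prompt is built in the Appendix C order, the photo can inflate reported label attention, and the photo and label items can prime the field Duke liking and satisfaction ratings in the message arms. Those two sets of field outcomes may then overstate the effect of a label met in ordinary use, chiefly against the no-message arm. Comparisons with the neutral arm are better protected.

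The dose is at most about 28 prompted views over 14 days, assuming two photo prompts a day and a photo at each. The size of any resulting bias cannot be derived from the documents. The conclusion also assumes that the photo usually shows the front of the pack. The point does not undermine the trial, but the change is worth making because the attention outcome has no other measure and order effects common to everyone cannot be removed later.

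**What to change.** 1. Reorder the prompt: recent-cigarette context and Duke items first, label-attention items second, pack photo last.
2. Add to the attention items an instruction such as *not counting times we asked you to photograph the pack*.
3. Reconcile Section 11.4, Appendix C and Appendix D on prompt timing, photo frequency and where the label items sit. The occasional random photo already described in Appendix D would serve, and would also reduce carry-over between prompts.

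The first two changes are REDCap order and wording edits and lose no data. The third costs some compliance photos if the occasional schedule is adopted. Replacing field photos with on-camera checks at Sessions 2 and 3 is not needed: it would confine verification to two scheduled moments that participants can anticipate. Some reactivity from asking about the label will remain whatever the order.
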